7. PARTICIPANT IDENTIFICATION

7.1 Trial Participants

Healthy male and female volunteers will be screened for inclusion and exclusion criteria and randomised to one of 5 treatment groups in case of eligibility.

60 subjects will be enrolled if all of the following inclusion criteria and none of the following exclusion criteria apply:

7.2 Inclusion Criteria

1. Signed informed consent obtained before any trial-related activities
2. Healthy men or women aged 18 to 55 years on the day of consenting
3. Ability to comprehend the full nature and purpose of the study, including possible risks and side effects; ability to cooperate with the investigator and to comply with the requirements of the entire study
4. All female subjects must have a negative serum pregnancy test at screening
5. Willingness not to become pregnant or to father a child during the entire study period by practicing reliable methods of contraception as specified in protocol section 8.11.4
6. Availability during the duration of the trial

7.3 Exclusion Criteria

The subject may not be enrolled in the study if any of the following applies:

1. Participation in another clinical study (including exposure to an investigational medicinal product or device) within one month before the screening visit or planned concurrent participation in another clinical study before completion of the treatment period (day 56)
2. History of immunodeficiency, known human immunodeficiency virus (HIV) infection or current hepatitis B/C infection
3. History of drug addiction including alcohol dependence within the last 2 years
4. Inability or unwillingness to avoid intake of more than around 20g alcohol per day during 48 hours after each vaccination (equals roughly 0.5 L beer or 0.25 L of wine)
5. Vaccination within 4 weeks prior to first vaccination or planning to receive any non-study vaccine until end of treatment period (day 56)
6. Prior receipt of any Chikungunya vaccine
7. History of moderate or severe arthritis or arthralgia within the past 3 months prior to Screening Visit
8. Recent infection within 1 week prior to Screening Visit (possibility of deferral)

9. Blood donations including plasma donations, 90 days prior to Screening Visit and anticipated blood, plasma, tissue, sperm or organ donation, throughout the study until end of treatment period (day 56)
10. Clinically relevant history of renal, hepatic, gastrointestinal, cardiovascular, respiratory, skin, haematological, endocrine, inflammatory, autoimmune or neurological diseases or clinically relevant abnormal laboratory values, that in the opinion of the investigator may interfere with the aim of the study
11. History of neoplastic disease (excluding non-melanoma skin cancer that was successfully treated) within the past 5 years or a history of any haematological malignancy
12. Behavioural, cognitive, or psychiatric condition that in the opinion of the investigator affects the ability of the participant to understand and cooperate with the study protocol
13. History of severe adverse reactions to vaccine administration, including anaphylaxis and related symptoms, such as urticaria, respiratory difficulty, angioedema and abdominal pain to vaccines, or history of allergic reaction likely to be exacerbated by any component of the vaccine
14. History of anaphylaxis to drugs or other allergic reactions, which the investigator considers compromising the safety of the volunteer
15. Use of medication during 2 weeks before the first vaccination and throughout the study, which the investigator considers affecting the validity of the study, except hormonal contraception or hormonal replacement therapy in female subjects. (Prior to taking any medication within 72 h before study vaccination, the subject should consult the investigator)
16. Use of immunosuppressive drugs like corticosteroids (excluding topical preparations) within 30 days prior to the first vaccination or anticipated use before completion of the treatment period (day 56)
17. Receipt of blood products or immunoglobulins within 120 days prior to the Screening Visit or anticipated receipt of any blood product or immunoglobulin before completion of the treatment period (day 56)
18. Pregnancy (positive pregnancy test at screening or during the treatment period) or lactation at screening, or planning to become pregnant during the treatment period
19. Unreliable contraception methods (for details please refer to protocol section 8.11.4)
20. Persons in a direct relationship with the sponsor, an investigator or other study team members. Direct dependent relationships include close relatives (i.e. children, parents, partner/spouse, siblings) as well as employees of the study site or the sponsor

8. TRIAL PROCEDURES

8.1 Informed Consent

Before any trial specific procedures are performed subjects will be informed about the exact nature of the trial, what it will involve for the participant, all procedures as determined by the clinical protocol, the known side effects and any risks involved in taking part. It will be clearly stated that the subject is free to withdraw from the trial at any time for any reason without prejudice to future care, without affecting their legal rights and with no obligation to give the reason for withdrawal.

The participant will be allowed as much time as needed to consider the information, and the opportunity to question the investigator or other independent parties to decide whether they will participate in the trial.

Written informed consent will then be obtained by means of participant's dated signature and dated signature of the qualified and experienced person who presented and obtained the informed consent. A copy of the signed informed consent will be provided to the subject and the original signed form will be retained at the site.

8.2 Randomisation

At Visit 1 (day 0) 60 eligible subjects will be randomly assigned to one of five treatment groups (A, B, C, D or E) by means of randomisation envelopes provided by data management.

Each subject will be assigned a unique three-digit randomisation number, stated on the envelope in ascending order. Only trained members of the unblinded study team will be authorised to open one envelope per subject, containing the information about the allocated treatment group.

Upon opening, the randomisation envelope shall be signed with date and time of randomisation and the number of the randomised subject shall be written down on it.

All 60 subjects will be equally distributed between the 5 groups using a randomisation ratio of 1 : 1 : 1 : 1 : 1 = A : B : C : D : E

A subject will be considered enrolled once the first IMP administration has been performed according to randomisation.

8.3 Blinding and Code-breaking

As this study will be conducted in an observer-blinded manner, unblinded study team members responsible for randomisation, preparation and administration of IMP, will otherwise not be involved in the conduct of the study.

All subjects, the investigator and site personnel performing study related assessments, as well as the sponsor's representatives involved in the monitoring and conduct of the study, will be blinded to treatment assignment.

Besides one set of randomisation envelopes, the site will receive an additional set of emergency envelopes stored in the ISF for unblinding purposes. As the knowledge of the subject's treatment might become mandatory (e.g. in case of emergency) the investigator has the possibility to open the emergency envelope identified with the subject's randomisation number and unblind the subject.

Please note that this code-breaking should only be done by the investigator if the knowledge of the subject's treatment influences the decision on further procedures. If unblinding would not make any difference for further treatment, the study team should remain blinded.

8.4 Screening Procedures

8.4.1 Screening Visit, (VS, 1-28 days prior to Visit 1)

After subjects have signed the informed consent form the screening visit will be performed within four weeks prior to Visit 1.

During this visit, all subjects will be checked for inclusion and exclusion criteria, undergo a full physical examination and evaluation of vital signs (systolic and diastolic blood pressure, pulse rate and body temperature). Medical history, vaccination history (covering the last three years prior to screening), prior/concomitant medication within 30 days prior to screening and demographic data will be recorded.

Blood and urine samples will be collected for clinical laboratory assays (HIV, hepatitis B and C, haematology, coagulation parameters, clinical chemistry and urinalysis). HIV tests with available results performed up to 30 days before screening are acceptable. For details on laboratory sampling and testing, see section 8.11.1.

A serum β -HCG pregnancy test will be performed in all women.

All subjects eligible for the clinical study will be asked to return to the study site within 28 days after the screening visit for Visit 1.

8.5 Treatment Period

8.5.1 Visit 1 (day 0)

Subjects found to be eligible will return to site for Visit 1 within 28 days after the screening visit. Inclusion and exclusion criteria will be checked again and (in case of changes since the screening visit) the medical history will be updated. Symptom-directed physical examination, system-based assessment (only if necessary according to findings in symptom-directed physical exam) and vital signs (systolic and diastolic blood pressure, pulse and body temperature) will be recorded. In addition, the subjects will be asked regarding changes in

concomitant medications since the last visit. A serum pregnancy test will be performed in all women.

Blood samples for baseline immunogenicity assessments (measles and Chikungunya antibody ELISA, PRNT₅₀) and isolation of serum for passive transfer will be drawn from an appropriate forearm or cubital vein. For T-cell assays blood samples will be collected and peripheral blood mononuclear cells (PBMCs) will be prepared. For details on laboratory sampling and testing, see section 8.11.

Subjects will be randomised to treatment group A, B, C, D or E and receive their first MV-CHIK vaccination.

The subjects' diaries will be explained and handed over. Subjects will be asked to report their body temperature and any adverse event in these diaries for 7 days, starting 6 hours after the injection.

After observation of the subjects for two hours, local reactions and adverse events (if any occurred) will be recorded.

Blood pressure and pulse rate will be checked, and participants will be discharged only if the investigating physician considers it to be safe for them to leave the department.

The subjects are invited to return to study site for Visit 2 on study day 14 (\pm 1 day).

8.5.2 Visit 2 (day 14 \pm 1 day)

Subjects will be requested to return to site for Visit 2, 13 to 15 days after the first vaccination.

The investigator or designee will assess local tolerability (of previous vaccination site) and ask about any new concomitant medications or AEs occurred since the last visit. The subject's diary will be collected and checked for completeness.

A blood sample will be collected and PBMCs will be prepared for T cell analysis.

The subjects will be asked to return to study site for Visit 3 on study day 28 (\pm 5 days).

8.5.3 Visit 3 (day 28 \pm 5 days)

Subjects will be invited to return to site for Visit 3, 23 to 33 days after Visit 1.

The investigator or designee will examine local tolerability (of previous vaccination site) and ask about any new concomitant medications or AEs occurred since the last visit.

In addition, symptom-directed physical examination, system-based assessment (only if necessary according to findings in symptom-directed physical exam) and vital signs (systolic and diastolic blood pressure, pulse rate and body temperature) will be recorded.

A serum pregnancy test will be performed in all women.

Blood samples will be taken for clinical chemistry, haematology and coagulation parameters and a urine sample will be collected for urinalysis.

Additional blood samples for immunogenicity assessments (measles and Chikungunya ELISA, PRNT₅₀) and isolation of serum for passive transfer will be drawn from an appropriate vein. For T-cell assays blood samples will be collected and PBMCs will be prepared. For details on laboratory sampling and testing, see section 8.11.

Subjects will receive their second vaccination of MV-CHIK or placebo, according to their randomised treatment group.

The subjects' diaries will be explained and handed over. Subjects will be asked to report their body temperature and any adverse event in these diaries for 7 days, starting 6 hours after the injection.

After observation of the subjects for two hours, local reactions and adverse events (if any occurred) will be recorded.

Blood pressure and pulse rate will be measured, and participants will be discharged only if the investigating physician considers it to be safe for them to leave the department.

The subjects are invited to return to study site for Visit 4 on study day 42 (\pm 5 days).

8.5.4 Visit 4 (day 42 \pm 5 days)

Subjects will be asked to return for Visit 4, 37 to 47 days after Visit 1.

The investigator or designee will assess local tolerability (of previous vaccination site) and ask about any new concomitant medications or AEs occurred since the last visit. The subject's diary will be collected and checked for completeness.

A blood sample will be collected and PBMCs will be prepared for T cell analysis.

The subjects are invited to return to study site for Visit 5 on study day 56 (\pm 5 day).

8.5.5 Visit 5 (day 56 \pm 5 days)

Subjects will be asked to return to site for Visit 5, 51 to 61 days after Visit 1.

The investigator or designee will examine and document local tolerability (of the previous vaccination site) and ask about any new concomitant medications or AEs occurred since the last visit.

Symptom-directed physical examination, system-based assessment (only if necessary according to findings in symptom-directed physical exam) and vital signs (systolic and diastolic blood pressure, pulse rate and body temperature) will be recorded. A serum pregnancy test will be performed in all women.

Blood samples will be taken for clinical chemistry, haematology, coagulation parameters and urine samples will be collected for urinalysis.

Additionally, blood samples for immunogenicity assessments (measles and Chikungunya ELISA, PRNT₅₀) and isolation of serum for passive transfer will be drawn from an appropriate

vein. For T-cell assays blood samples will be collected and PBMCs will be prepared. For details on laboratory sampling and testing, see section 8.11.

Upon Visit 5, the treatment period of this study will be completed. Subjects will be allowed to participate in other clinical trials after all procedures of Visit 5 will have been performed.

Blood pressure and pulse rate will be measured before participants will be discharged, and subjects are invited to return to study site for follow up Visit 6 on study day 182 (\pm 14 days).

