6.2 Study Endpoints

6.2.1 Primary Endpoint

- Immunogenicity 28 days after the last MV-CHIK vaccination confirmed by the presence of functional antibodies as determined by the plaque reduction neutralisation test (PRNT₅₀)

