11.7 Subject Diary

The subjects will be instructed to complete a diary for 7 days after each vaccination to document local and systemic tolerability as well as body temperature.

Solicited local and solicited systemic AEs will be assessed by the subjects themselves by checking for presence of the listed symptoms and measuring the size of the affected area where appropriate (a template will be provided for local reaction grading, as shown in Appendix 1). The diary will also provide space for recording unsolicited AEs and concomitant medication.

Recording should be done approximately at the same time each day, starting on the day of vaccination. The first entry should be made 6 hours ± 1 h after vaccination at Visit 1 and Visit 3.

The subjects' diaries will be collected and verified for completeness by the investigator at Visit 2 and Visit 4. Any AE recorded in the subject diaries will be entered in the eCRF by the investigator or authorised delegates. The investigator will re-evaluate the severity of the reported local and systemic AEs according to the below Tables 5 and 6.

Diary solicited systemic AEs include: nausea, vomiting, headache and fatigue, also to be documented in the eCRF.

In addition, body temperature will be recorded daily for 7 days and fever will be graded by the investigator according to the FDA Guidance for Industry. For details see below Table 6.

Table 5: Grading of Local Reactions

Local reaction to injectable product	Mild (grade 1)	Moderate (grade 2)	Severe (grade 3)	Potentially life threatening (grade 4)
Pain	Does not interfere with activity	Interfere with activity or repeated use of non-narcotic pain reliever	Prevents daily activity or repeated use of non-narcotic pain reliever	Emergency room (ER) visit or hospitalisation
Tenderness	Mild pain to touch	Pain with movement	Significant pain at rest	ER visit or hospitalisation
Erythema/ Redness¹	≤ 5 cm	5.1–10 cm	> 10 cm	Necrosis or exfoliate dermatitis
Swelling²	≤ 5 cm and does not interfere with activity	5.1–10 cm or interfere with activity	> 10 cm or prevents daily activity	Necrosis
Itching	Does not interfere with activity	Interferes with activity or repeated use of non-narcotic pain reliever	Prevents daily activity or repeated use of anti-inflammation and pain-relieving ointment	Emergency room (ER) visit or hospitalisation

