2.9 Protocol Deviations

Protocol deviations will be collected only for the preliminary analysis. A listing of the potential protocol deviations will be prepared by Assign Data Management and Biostatistics GmbH using information from the eCRF documentation and monitoring reports. These protocol deviations will be classified into major or minor protocol deviations based on their possible impact on the study results in a Blind Data Review Meeting (BDRM) prior to the preliminary analysis attended by Assign Data Management GmbH and Themis Bioscience GmbH (sponsor).

Major protocol deviations will include but are not limited to the following:

- Subjects with any confirmed immunosuppressive or immunodeficient condition, including human immunodeficiency virus (HIV), hepatitis A, B or C infection or a family history of congenital or hereditary immunodeficiency
- Subjects who received the wrong or no IMP
- Subjects who received less than the protocol-defined number of vaccinations
- Subjects who received a wrong dose other than they were randomized to
- Subjects who entered the study even though they did not satisfy the entry criteria
- Subjects with substantial time window violations on vaccination visits
- Subjects who received an forbidden prior or concomitant medication
 - Immunosuppressive drugs: Use of corticosteroids (excluding topical preparations) or immunosuppressive drugs within 30 days prior to first IMP administration, or anticipated use during the trial
 - Treatments with non-study licensed vaccines within 4 weeks prior to first study vaccination until the end of the treatment period (day 56)
 - Receipt of blood products or immunoglobulins within 120 days prior to the Screening Visit or anticipated receipt of any blood product or immunoglobulin before completion of the treatment period (day 56)
- Further protocol deviations that could impact immune response that have not been described above

Adapted from:

STAT03_A Statistical Analysis Plan

Version 6.0, Effective Date 16-Feb-2018

Confidential and intellectual property of Assign DMB. No part of this document or its contents may be duplicated, referenced, published or otherwise disclosed in any form or by any means without prior written consent of Assign DMB.

Page 12 of 29

06CJDX

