5.2 Derivations and Definitions

- For the preliminary analysis, only PRNT₅₀ will be analyzed included time points Visit 1 (day 0), Visit 3 (day 28) and Visit 5 (day 56). For the final analysis all immunogenicity parameters will be analyzed at all available time points except passive transfer.
- Analysis of passive transfer results are not described in this SAP.
- The primary analysis compares the PRNT₅₀ titer 28 days after last MV-CHIK vaccination between treatment groups. Therefore, titers from Day 56 in Groups A-D will be considered and the titer at Day 28 for Group E.
- Seroconversion rate for anti-Chikungunya PRNT₅₀ titers is defined as proportion of subjects achieving anti-Chikungunya PRNT₅₀ titers ≥ 10 at a certain time point.
- Seroconversion rate for Chikungunya-ELISA is defined as proportion of subjects achieving Chikungunya-ELISA titers ≥ 16 at a certain time point.
- The lower limit of quantification (LLOQ) are not known for immunogenicity parameters at SAP development and therefore the following general rules will apply:
 - In data listings, the original reported value “<LLOQ” will be displayed.

Adapted from:

STAT03_A Statistical Analysis Plan

Version 6.0, Effective Date 16-Feb-2018

Confidential and intellectual property of Assign DMB. No part of this document or its contents may be duplicated, referenced, published or otherwise disclosed in any form or by any means without prior written consent of Assign DMB.

Page 15 of 29

06CJDX

- For calculations the half of the true LLOQ value will be used for such values.

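### Visits 4 and 5 are counted from Visit 1, not from the second injection, so the primary sample in Groups A–D may fall 18 to 38 days after the last MV-CHIK dose (Group E: 23 to 33) and the second 7-day diary may be collected before it is complete

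*Combined protocol and SAP*

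**What the plan says.** Protocol 8.5.3 places the second injection visit thus: "Subjects will be invited to return to site for Visit 3, 23 to 33 days after Visit 1". At that visit, "Subjects will receive their second vaccination of MV-CHIK or placebo, according to their randomised treatment group". Protocol 8.5.4 then states "Subjects will be asked to return for Visit 4, 37 to 47 days after Visit 1", and 8.5.5 states "Subjects will be asked to return to site for Visit 5, 51 to 61 days after Visit 1". Table 2 and SAP 1.6 repeat these as study-day windows of ±5 days. No section ties Visit 4 or Visit 5 to the actual date of the second injection or sets a minimum gap after it.

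The primary endpoint (Protocol 6.2.1, SAP 1.3.1) is "Immunogenicity 28 days after the last MV-CHIK vaccination confirmed by the presence of functional antibodies". SAP 5.2 implements it by visit: "titers from Day 56 in Groups A-D will be considered and the titer at Day 28 for Group E".

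On safety, Protocol 11.7 says "The subjects will be instructed to complete a diary for 7 days after each vaccination". Entries start on the day of vaccination, and the second diary is collected at Visit 4. Protocol 11.5 promises 28 days of follow-up after each injection, while 10.2 ends adverse-event recording at Visit 5.

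The only timing item in the SAP 2.9 list of major deviations is "Subjects with substantial time window violations on vaccination visits", with no limit in days. Visit 5, which supplies the primary sample in Groups A–D, is not a vaccination visit.

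**The concern.** The primary endpoint is defined by time since the last MV-CHIK dose, but in Groups A–D the sampling visit is defined by time since the first. The tolerance on Visit 3 and the tolerance on Visit 5 therefore add up. In Group E the primary sample is taken at Visit 3 after a single dose, so only one tolerance applies. The same endpoint is held to different timing in the arms being compared, and the ANOVA, whose only factor is treatment group, does not account for it.

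The same stacking reaches the safety data. A late Visit 3 followed by an early Visit 4 can cut the second diary short, and a late Visit 3 followed by an early Visit 5 shortens the follow-up that Protocol 11.5 describes. A subject at any of these extremes has complied with every visit window.

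**Working it through.** **Inputs.** Visit 3, 4 and 5 windows from Protocol 8.5.3–8.5.5; diary length and start day from 11.7; primary sample by group from SAP 5.2.

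**Stated windows.** 28 ± 5 = 23–33; 42 ± 5 = 37–47; 56 ± 5 = 51–61. All three match the text.

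**Interval after the second injection.** Minimum = earliest later visit − latest Visit 3. Maximum = latest later visit − earliest Visit 3.

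| Interval | Minimum | Maximum | Nominal |
|---|---|---|---|
| Visit 5 − Visit 3 (primary sample, A–D) | 51 − 33 = 18 | 61 − 23 = 38 | 28 |
| Visit 4 − Visit 3 | 37 − 33 = 4 | 47 − 23 = 24 | 14 |
| Visit 3 − Visit 1 (primary sample, E) | 23 | 33 | 28 |

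The primary sample is thus allowed ±10 days in A–D and ±5 days in E.

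**Diary.** Seven daily entries starting on the day of injection fall on post-injection days 0 to 6. With Visit 3 on day 33 and Visit 4 on day 37, collection is on post-injection day 4. Entries for days 0–4 can then exist, so at most 5 of 7 (4 if the visit precedes that day's entry). The first diary is safe, because Visit 2 is 13–15 days after the first injection.

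**Adverse-event follow-up.** Recording stops at Visit 5, so it can end 18 days after the second injection, against the 28 days in 11.5.

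**How much of the permitted range is affected.** There are 11 × 11 = 121 in-window day pairs. For Visits 3 and 5, 30 of 121 (24.8%) lie outside 23–33 days after the second injection and 91 lie inside. For Visits 3 and 4, 3 of 121 put collection before the seventh entry. These counts describe the windows; they do not forecast attendance.

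**Spread, assuming visit days uniform and independent.** The SD of one 11-day window is √[(11² − 1)/12] = √10 = 3.2 days (Group E). The SD of the difference of two such windows is √(10 + 10) = √20 = 4.5 days (A–D).

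**Effect on titre, for scale only.** Assume a post-peak half-life of 20–60 days and a between-subject SD of 0.4–0.6 log₁₀; neither is in the documents. Timing then contributes 4.5 × 0.301/60 = 0.02 to 4.5 × 0.301/20 = 0.07 log₁₀. At worst the total SD is √(0.4² + 0.067²) = 0.406, a rise of about 1.4%.

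**Windows counted from the second injection with the same ±5 days.** Visit 4: 14 ± 5 = 9–19 days, after the last diary entry. Visit 5: 28 ± 5 = 23–33 days, the same as Group E.

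**The case against.** The strongest reply is that study-day windows are an ordinary choice in a trial of 12 subjects per arm with no formal sample size calculation, and that the consequences are small. Much of this stands. Four stronger readings are tempting, and the documents do not support them.

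- *That A–D and E are biased against each other.* Both intervals centre on 28 days. The windows alone create unequal spread, not a shift.
- *That timing could move titres 1.26- to 2.0-fold.* Those figures are 2^(20/60) and 2^(20/20). They compare two single subjects at opposite ends of the 20-day span under the assumed half-life, and say nothing about a GMT ratio. Protocol 4.4.1 also reports that neutralising antibodies persisted through the phase I study, which fits poorly with a 20-day half-life.
- *That more reactogenic groups will have later second injections.* SAP 6.2.2 has a category for a second administration delayed because of an adverse event. This shows that a delay can be recorded, not that delays are expected or differ by dose.
- *That any mistimed Visit 5 sample stays in the per-protocol set.* The SAP 2.9 list is open-ended, has a catch-all for deviations affecting immune response, and allows blinded case-by-case decisions. Only the narrower point holds: a Visit 5 inside its window but far from 28 days after the second injection is not a listed deviation.

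The diary extreme is rare among the permitted pairs. Completeness is checked at collection, and adverse events are also asked about at each visit through Visit 5. T-cell results are only listed (SAP 5.1), so no planned group comparison depends on the timing of Visit 4.

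None of this removes the mismatch between the visit windows and the endpoint, the diary and the 28-day follow-up.

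**Conclusion.** The point holds as an inconsistency in the protocol's own figures. The 18–38 and 4–24 day ranges need no assumption beyond full compliance with the windows. How often the extremes would occur is not known from the documents.

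For the primary comparison, the likely consequence is a small loss of precision in A–D. The 4.5 against 3.2 day contrast rests on uniform, independent visit days, and the estimate of at most about 1.4% on the SD rests further on the assumed half-life and between-subject SD. For safety, the consequence is a possible truncated second diary and follow-up shorter than stated. The change is worth making because it is cheap and specific, not because the results are at serious risk.

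**What to change.** In Protocol 8.5.4, 8.5.5 and Table 2, and in SAP 1.6, count the Visit 4 and Visit 5 assessment windows from the actual date of the second injection, keeping ±5 days. The vaccination schedule is unchanged. Reconcile these windows with the 7-day diary in 11.7 and the follow-up in 11.5. The shortest follow-up becomes 23 days, not 18, so it is nearer to 28 but the wording of 11.5 still needs to agree with it.

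In the SAP, derive days since the last MV-CHIK injection from the injection and sample dates already listed (SAP 7.2, Listings 1.3.1, 1.4.1 and 1.4.2) and summarise it by group. Add a sensitivity analysis of the primary comparison restricted to samples 23–33 days after the last MV-CHIK injection. This should not become a blanket per-protocol exclusion: under the present windows it could remove compliant subjects, about 48 × 30/121 ≈ 12 of the 48 in A–D if visit days are uniform and independent.

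The cost is a wording change, one derived variable and one extra analysis, with no added visits. The downside is that Visit 5 could fall on days 23 + 23 = 46 to 33 + 33 = 66 from Visit 1, instead of 51–61. That slightly widens the timing of Group E's day-56 secondary sample, which is counted from its single dose.
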